#### **14.5 Study Records Retention**

According to the University of North Carolina at Chapel Hill's Archives and Record Management Services schedule for General Records Retention and Disposition Schedule 6.10, records will be kept for 5 years after the completion of the study or grant end date, whichever is later.

## 14.6 Protocol Deviations

All deviations from the protocol will be addressed in study participant source documents. The researcher will complete a Protocol Deviation Log (*Appendix O*) using the participant code as the identifier. This form will collect information such as the date the deviation occurred, details of what the deviation consisted of, any corrective and preventative actions that were taken as a result of the deviation, and the date that the PI and IRB were notified. The PI will review the information and initial once approved. A completed copy of the Protocol Deviation Form will be maintained in the regulatory file, as well as in the participant's source document. Protocol deviations will be sent to the IRB per their guidelines. The site PI/study staff will be responsible for knowing and adhering to their IRB requirements.

## **15 PUBLICATION POLICY**

This study will be registered on clinicaltrials.gov once IRB approved. There are no restrictions on publications since this is an investigator-initiated study funded by a grant agency (NIMH) that has no influence on the publications resulting from this study. The aim is to publish the results of this study in a peer-reviewed, highly-ranked psychiatry journal.

## SUPPLEMENTS/APPENDICES

### APPENDIX A: SCHEDULE OF EVENTS

A detailed schematic describing all visits and assessments.

STILL 2 Study Outline							
						1 Month Follow-up	
						1 Week Follow-up	
Procedures							
Signed Consent Form	X						
Vital Signs		X	X	X	X	X	X
SCID, Med Hx, Phys. Exam		X					
Incl/Excl Criteria		X					
Medications							
AHRS	X	X	X		X	X	X
PANSS, CGI-S			X		X		X
SAS, AIMS		X			X		X
BACS			X		X		X
UDS, beta-HCG		X					
Randomization			X				
Stimulation			X	X	X		
EEG		X			X	X	X
EEG Questionnaire		X			X	X	X
Adverse Events			X	X	X		

## APPENDIX B: AE REPORT FORM

## Adverse Effects Report:

*Reasons for Report (adverse event, time, date and place of occurrence if available):*

1. What do we already know about the therapy?
  - a.
2. What is the temporal relationship of the AE to the study therapy?
  - a.
3. Does the AE improve or disappear when the therapy is stopped?
  - a.
4. Is the AE a worsening of baseline symptom(s)?
  - a.
5. Is the AE a result of an underlying concurrent medical condition(s) or concurrent medication(s)?
  - a.
6. Additional Information provided by research team
  - a.

Research team member signature \_\_\_\_\_

Date

---

**Co-Investigator :**

---

---

---

---

---

### Steps to be taken (if applicable)

---

---

---

## APPENDIX C: AE LOG

## APPENDIX D: SAE REPORT FORM

Participant ID: \_\_\_\_\_

1. Location of SAE (e.g., clinic, home): \_\_\_\_\_
2. Age: \_\_\_\_\_
3. Gender: Male Female
4. SAE term (provide diagnosis): \_\_\_\_\_
- 4a. If diagnosis is not known, symptoms: \_\_\_\_\_
5. Date of onset: \_\_\_\_\_ (dd/mm/yyyy)
6. What is the severity grade of the serious adverse event?

- Grade: 1: Mild
- Grade 2: Moderate
- Grade 3: Severe
- Grade 4: Life-threatening
- Grade 5: Death

7. Did the participant receive the investigational product or study intervention prior to this SAE?  
 Yes     No     N/A

7a. If yes, identify the investigational product or study intervention received prior to the SAE:  
Investigational Product/Study Intervention

Dose \_\_\_\_\_  
Units \_\_\_\_\_  
Frequency \_\_\_\_\_

Start Date \_\_\_\_\_ / \_\_\_\_\_ / \_\_\_\_\_ (dd/mm/yyyy)  
Stop Date \_\_\_\_\_ / \_\_\_\_\_ / \_\_\_\_\_ (dd/mm/yyyy)  
Check if Ongoing

8. Action taken with investigational product/study intervention:

- Continued
- Lowered
- Interrupted
- Discontinued
- Increased
- N/A

9. Outcome of SAE:

- Ongoing at this time
- Resolved without sequelae
- Resolved with sequelae
- Death
- Present at death, not contributing to death

10. Date of resolution: \_\_\_\_\_ (dd/mm/yyyy) or  
 Ongoing at end of study

11. Seriousness criteria? (Check all that apply)

- Life-threatening
- Required hospitalization or
- Prolongation of existing hospitalization
- Congenital anomaly
- Disabling/incapacitating
- Important medical event
- Fatal

If fatal: 11a. Date of death: \_\_\_\_\_ (dd/mm/yyyy)

11b. Primary cause of death: \_\_\_\_\_

11c. Was an autopsy performed?

- Yes
- No

12. Relationship to investigational product/study intervention:

- Related (Associated with the use of the study intervention. There is a reasonable possibility that the experience may have been caused by the study intervention.)
- Unrelated

13. If SAE is unrelated to investigational product/safety intervention, select all possible etiologies: Concurrent illness, disease, or other external factors, specify:

---

---

Concurrent medication, specify:

---

Secondary study procedure, specify:

---

Accident, trauma, or other external factors, specify:

---

Other, specify:

---

14. Did the participant receive any relevant concomitant medications in response to the SAE?

- Yes
- No

14a. If yes, please specify: Name, Start and Stop date or On going

---

15. Did the participant receive any treatments/procedures in response to the SAE?

- Yes
- No

15a. If yes, please specify

---

---

16. Did the participant receive relevant laboratory or diagnostic tests in response to the SAE?

Yes  
No

16a. If yes, provide the name of the test and results with normal ranges and/or supplemental exams below:

---

---

---

17. Narrative/Comments (provide a description of the serious adverse event including chronological clinical presentation and evolution of the serious adverse event and associated signs/symptoms):

---

---

---

---

---

---

---

---

---

---

---

---

---

---

---

---

---

---

---

---

---

---

---

---

18. Completion of form: printed names, signatures and date of signature

*Person Completing Form*  
(print name)

*Person Completing Form*  
(signature)

*Date*

*Investigator (print name)*

*Investigator (signature)*

*Date*

---

## APPENDIX E: UE/SAE LOG

Participant ID	Date Event Occurred	Date Study Team Notified of Event	Event	Date Reported to IRB	Study SAE Form Completed
				 Yes  No  N/A	
				 Yes  No  N/A	
				 Yes  No  N/A	
				 Yes  No  N/A	
				 Yes  No  N/A	
				 Yes  No  N/A	
				 Yes  No  N/A	
				 Yes  No  N/A	
				 Yes  No  N/A	
				 Yes  No  N/A	
				 Yes  No  N/A	
				 Yes  No  N/A	
				 Yes  No  N/A	

**APPENDIX K: ENROLLMENT LOG**

Subject ID	Date Consent Signed	Gender	Race	Ethnicity	Treatment Arm / Group	Explanation if subject did not complete study / Comment
1		M  F 				
2		M  F 				
3		M  F 				
4		M  F 				
5		M  F 				
6		M  F 				
7		M  F 				
8		M  F 				
9		M  F 				
10		M  F 				
11		M  F 				
12		M  F 				
13		M  F 				
14		M  F 				
15		M  F 				

## APPENDIX L: INCLUSION/EXCLUSION CRITERIA CHECKLIST

Inclusion Criteria		
DSM-IV diagnosis of schizophrenia, any subtype, or schizoaffective disorder, with refractory auditory hallucinations. Duration of illness >1 year.	Yes	No
18-70 years old.	Yes	No
Clinically stable for at least 12 weeks, i.e. not requiring hospitalization or a change in level of care	Yes	No
On current antipsychotic doses for approx. 4 weeks or more	Yes	No
Capacity to understand all relevant risks and potential benefits of the study (informed consent) OR has a legal guardian who can complete consent forms on the patients behalf	Yes	No

Exclusion Criteria		
Subjects with a DSM-IV diagnosis of alcohol or substance abuse (other than nicotine) within the last month or a DSM-IV diagnosis of alcohol or substance dependence (other than nicotine) within the last 6 months	Yes	No
History of significant head injury/trauma, as defined by loss of consciousness for more than 1 hour, or recurring seizures, or requiring later cognitive rehabilitation or causing cognitive sequelae	Yes	No
Prior brain surgery	Yes	No
Any brain devices/implants, including cochlear implants and aneurysm clips	Yes	No
Co-morbid neurological condition (i.e. seizure disorder, brain tumor)	Yes	No
Medical or neurological illness (unstable cardiac disease AIDS, malignancy, liver or renal impairment) or treatment for a medical disorder that could interfere with study participation	Yes	No
Non English speakers	Yes	No
Pregnancy, nursing, or if female and fertile, unwilling to use appropriate birth control measures during study participation	Yes	No

*If the responses to all the inclusion criteria are YES and all the exclusion criteria are NO, the participant is able to participate in the trial.*

Is the participant eligible to participate in the trial?

If NO, discontinue subject.

If YES, I have reviewed the inclusion and exclusion criteria and have determined that the participant is eligible for participation in the trial.

Investigator Signature:

Date:

## APPENDIX M: NOTE TO FILE

IRB#: 14-3285

Study Title:

PI: [name]

Date of Occurrence: \_\_\_\_\_

Research Name: \_\_\_\_\_

Participant ID: \_\_\_\_\_

Reason for Note:

\_\_\_\_\_

Note:

\_\_\_\_\_

\_\_\_\_\_

\_\_\_\_\_

\_\_\_\_\_

\_\_\_\_\_

\_\_\_\_\_

\_\_\_\_\_

\_\_\_\_\_

Corrective action (if applicable); \_\_\_\_\_

\_\_\_\_\_

\_\_\_\_\_

Signature: \_\_\_\_\_

Date: \_\_\_\_\_

## APPENDIX N: PROTOCOL DEVIATION LOG

## APPENDIX O: STUDY START UP CHECKLIST

### Study Start Up Checklist

Study Title: \_\_\_\_\_

Funding Source: \_\_\_\_\_

Date Completed	
CRMS Recorded Created	_____
IRB Application Submitted	_____
CVs/Certifications/Medical	_____
License	_____
IRB Roster	_____
IRB Statement of Compliance	_____
PI Signature of Protocol	_____
Date Completed	
Study Binders Created	_____
Regulatory Documents Filed	_____
Protocol Deviation Tracking Log Filed	_____
Completion of Site Training, Filed	_____
Delegation Log Completed	_____
Develop Recruitment Plan	_____
Begin Pre-Screening	_____
Source Documents Created	_____
Participant Folders Created	_____
_____	_____
_____	_____
Schedule Study Start Up Meeting	_____
Lab Kits Received	_____
Participant Supplies Received	_____
Investigational Device Received	_____
_____	_____

## APPENDIX P: PARTICIPANT OFF STUDY FORM

Participant Initials 

--	--	--

ID 

--	--	--	--	--

Date: 

--	--

 / 

--	--

 / 

--	--

Month

Day

Year

### Participant Off Study

Date participant went Off Study: 

--	--

 / 

--	--

 / 

--	--

Month

Day

Year

#### INDICATE OFF STUDY REASON:

- Study Activities Completed
- Side effects of study intervention (complete applicable SAE form or AE Tracking Log)
- Death
- Participant lost to follow-up\* (provide comments below)
- Participant refused follow-up\* (provide comments below)
- Other\* (provide comments below)
- Participant withdrew (complete Early Withdrawal section below)

Was treatment unblinded?  Yes  No  Not Applicable

### Early Withdrawal

Last Visit Completed:

Early Withdrawal form not completed

Screening Visit  
 Visit 1  
 Visit 2

Visit 3  
 Visit 4  
 Visit 5

Visit 6  
 Visit 7

Indicate the **primary** reason the participant has withdrawn from the study (select only one):

- Participant deemed eligible but declined participation
- Participant deemed inappropriate for study participation by the PI
- Participant was determined to be ineligible after enrollment\* (provide comments below)
- Identification of disease/condition after enrollment that warrants withdrawal\*
- Unable to continue due to personal constraints\*
- Side effects of study intervention \* (complete UWI-02-007 Adverse Event Tracking Log)
- Other \*

\*Additional explanation required:

---

---

**FORM COMPLETED BY:** \_\_\_\_\_

## APPENDIX Q: TELEPHONE LOG

Date/Time	Incoming/Outgoing	Message/Conversation	Reason for calling	Comments/Researcher Initials
	Incoming Outgoing	Message Conversation		

## APPENDIX R: TRAINING LOG

**Title of Training:** \_\_\_\_\_  
(e.g., Protocol; Amendment; IRB [include version #/date])

**DATE:** \_\_\_\_\_

By signing below, each staff member verifies they have been trained on the information and understand the obligations/responsibilities associated with this training.

Training Date (if different than above)	Trainee Name (please print)	Trainee Signature	Training Format (ie Presentation; Self-Study)

Trainer Name (if relevant): \_\_\_\_\_  
(Please print)

Trainer Signature (if relevant): \_\_\_\_\_

## APPENDIX S: TELEPHONE RECRUITMENT SCRIPT

Hello, my name is \_\_\_\_\_. Are you contacting me in regards to the non-invasive brain stimulation study?

If 'No', redirect them as necessary)

(If 'Yes', proceed)

Do you have time now to hear about the study, answer a few screening questions, and schedule your first visit?

(If 'No', ask for a good time to call back)

(If 'Yes', proceed)

Great! This study is looking at how abnormal rhythms of brain activity in schizophrenia respond to very weak applied currents. Findings from this study will help the development of treatments for the symptoms of schizophrenia, like auditory hallucinations. In the study, a very weak current will be applied to your scalp. Some people report a mild tingling because of this stimulation, but no other side effects have been found. It is not a shock and should cause no pain.

Participation in this study includes one to eight sessions, with one session being an initial information session, then five, twice daily stimulation sessions, followed by a one week then one month follow up session. The stimulation sessions need to be on consecutive days with the second session occurring 3 hours after the completion of the first session. The maximum compensation for this study is \$340 for completing all of the sessions. Are you still interested in participating?

(If 'No', thank them for their time)

(If 'Yes', proceed)

Great! In order to make sure you're eligible for the study, I need to ask you a few questions. Please answer yes or no. You do not need to provide any further details.

(If the answer given is not the same as the answer shown, thank the individual for his or her interest and say unfortunately, they do not qualify for the current study)

- Are you 18 years old or older? (Yes)
- Have you ever, or are you currently being treated for a neurological condition (i.e. epilepsy)? (No)
- Are you currently taking any benzodiazepines or anticonvulsant medications? (No)
- Have you ever had brain surgery? (No)
- Do you have any brain devices or implants, including a cochlear implant or aneurysm clip? (No)
- Have you ever been diagnosed with a traumatic brain injury? (No)

- (For females only), Is there a chance you may be pregnant? (No)

Follow-up questions:

- Do you wear glasses/contact lenses?
  - Could you bring your contact lenses for the study visits instead of wearing your glasses?

(If answered according to all indicated responses, continue)

Excellent! Due to the study schedule, some sessions will be longer than others. Is it possible for you to be available from 8 – 5 on weekdays to be at the UNC Hospital in order to participate in this study? If not, can you specify the days/times that do not work for you?

Would you be willing to participate in an 8 hour session for this study? (This includes a 3 hour break).

You are eligible for participation in the first session of the study. At the first session we will determine your eligibility for the remainder of the sessions. I'd like to schedule your first session now. It will last approximately 3 hours. All testing will be conducted at either UNC Hospital or the NCPRC in Raleigh. (specific location).

(Schedule a time for first session)

I will give you a call to confirm your appointment 24 hours beforehand. If you have any questions before then, please don't hesitate to contact us at this phone number.

Thank you for your time.

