*Risk of Injury and Discomfort:* Transcranial current stimulation has been used without any reports of serious side-effects for more than a decade. This stimulation mode has NOTHING to do with electroconvulsive therapy that applies many orders of magnitude higher stimulation current. Rather, transcranial current stimulation is so weak that it does not cause super-threshold activation of neurons ([name] and McCormick, 2010). In particular, tACS has been used without reports of any serious side-effects. Some participants report a transient mild tingling, burning, or itching underneath the electrodes and headache, but no other side effects have been noted. Importantly, it remains unclear

if these mild side-effects were caused by the transcranial brain stimulation. In order to monitor these side-effects, we will be administering an adverse effects stimulation questionnaire (*Attachments 1 &2*) after each stimulation session to determine whether these effects were experienced. Research personnel present during these sessions will also check in with the participant periodically during the stimulation to see whether they are comfortable. If any side-effect occurs (rated by the participant as stronger than “moderate”) or the participant is experiencing severe discomfort, the stimulation will be immediately stopped.

While not previously reported with tDCS or tACS in humans, there is a theoretical possibility that stimulation of neuronal circuits could lead to epileptic discharges. To minimize this occurrence, we screen and exclude patients with personal and family history of neurological conditions from the study. If abnormalities or a seizure is witnessed during the course of the study, the subject will be referred to a neurology clinic for further evaluation and treatment.

We have no evidence that our treatment paradigms will increase auditory hallucinations if not treated (receive the sham treatment), as participants, will be by definition, stable. If an enrolled patient shows signs of increase symptoms that were not apparent during enrollment, a referral to UNC Psychiatry will be made. [name], Co-I, will facilitate this process.

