Eligible participants who complete this clinical trial will have a total of 9 to 11 visits; an initial screening session, a 2nd screening session, (if needed) 2 more follow up screening sessions, 5 days of twice daily stimulation sessions, a one week and a one month follow up visit. The initial screening session will take approximately 2 hours, and each follow up screening session will take approximately 3 hours each. The first day of stimulation will take approximately 6 hours and days 2 through 4 of stimulation will take 4.5 hours each. The last day of stimulation will take about 9 hours. The one week follow up will take approximately 2.5 hours and the one month follow up will take approximately 5 hours. We estimate that total participant participation duration will be approximately 41 to 47 hours.

The primary objective is to conduct a pilot clinical trial to establish the feasibility of recruitment and implementation of the methodology and to collect preliminary efficacy data for the use of tACS by comparing AHRS scores immediately before the first stimulation session and

immediately after the last stimulation session in patients with schizophrenia or schizoaffective disorder. As a secondary objective we will assess the differential clinical effects of sham, 10 Hz and 2 mA tDCS on EEG measures of alpha oscillations.

In order to ensure symptom stability for each potential participant, there will be up to a 6 week period for the participant to achieve a stable AHRS score. The AHRS will be performed at 2 week intervals during screening. A stable score is defined as having less than or equal to 20% change. If the change between the first and second AHRS scores is less than or equal to 20%, then the participant will move on to the week of stimulation. If a stable score is not achieved at the second screening session, the participant will have two more opportunities at 2 week intervals during follow-up screening sessions to achieve a stable score. The participant will be paid for each session. If the participant does not achieve a stable score (if there remains a greater than 20% change in scores between consecutive AHRS administrations) by the end of the 6 weeks, the participant will not be eligible to continue participation.

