### 7.1 Screening

#### Screening Telephone Call

Individuals who are referred by a mental health care provider will be contacted by a researcher for an initial phone screening. Researchers will keep a Telephone Contact log for each telephone conversation with a participant throughout the study. There will be a log for each participant and will be filed in the participant binder (*Appendix R*).

During the telephone screening, researchers will provide a brief background about Schizophrenia and tACS. Any initial questions will be answered at this point. The timeline of visits will then be explained; there will be 1 to 8 sessions, with 1 initial session, 5 consecutive week days of twice daily stimulation, with follow ups one week after the last stimulation and one month after last stimulation. The participant will be informed that compensation for their participation will be received at each session throughout the study. The participant will be asked if they have any additional questions. Once all questions have been answered, the participant will be asked if he/she is still interesting in participating in the study. If yes, the researcher will begin the initial phone screening which will determine eligibility for the initial session. The screening questions are shown below. If the required answers are given for each question, the initial session will be scheduled and a reminder call will be given at least 24 hours before initial session. We will use the telephone script provided in *Appendix T* for all telephone screenings.

- Are you 18 years or older? (Yes)
- Have you ever, or are you currently being treated for a neurological condition (i.e. epilepsy)? (No)

- Have you ever had brain surgery? (No)
- Do you have any brain devices or implants, including a cochlear implant or aneurysm clip? (No)
- Have you ever been diagnosed with a traumatic brain injury? (No)
- For females only, is there a chance you may be pregnant? (No)

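### The telephone script tells every candidate that nothing beyond tingling has been found and counts at most eight sessions, which conflicts with the protocol's own list of reactions and with the 9 to 11 visits in Section 4

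*Combined protocol and SAP*

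**What the plan says.** Section 7.1 makes the script operative text: "We will use the telephone script provided in" an appendix, for all telephone screenings. (It cites Appendix T, but the script is Appendix S; Appendix T is the EEG questionnaire.)

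On side effects, the script says "Some people report a mild tingling because of this stimulation, but no other side effects have been found". Section 2.3.1 says "Some participants report a transient mild tingling, burning, or itching underneath the electrodes and headache", and Section 9.2.2 gives the same four reactions. Both sections add that no others have been noted and that it is unclear whether stimulation caused them. Section 2.3.1 also states that "there is a theoretical possibility that stimulation of neuronal circuits could lead to epileptic discharges", and says this has not been reported in humans.

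On burden, the script says "Participation in this study includes one to eight sessions" and itemises one initial session, five days of twice-daily stimulation, a one-week visit and a one-month visit. Section 7.1 tells callers the same. The Protocol Summary gives 1 to 8 visits in its précis and 8 visits for a completer. Section 4 says completers "will have a total of 9 to 11 visits", and Section 7 numbers the one-month follow-up as Visit 11.

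On the longest day, the script asks "Would you be willing to participate in an 8 hour session for this study". Section 4 says "The last day of stimulation will take about 9 hours", and the Protocol Summary gives the same length.

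**The concern.** A short recruitment script may leave things out. This one goes further and states that effects recorded elsewhere in the protocol have not been found. The script asks whether the caller is still interested immediately after this statement and the session count, so people decide on them. Eligible participants include some who enter through a legal guardian's consent.

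The visit count matters for a similar reason. The uncounted visits are screening visits spaced about two weeks apart, so a candidate who has planned for one initial session may not return for the second. The retention strategy in Section 5.3 relies on participants fully understanding the process and its duration, and the script works against that. What is at stake is the accuracy of what candidates are told before consent, and possibly some loss during screening. No endpoint, analysis, allocation or power figure depends on it.

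**Working it through.** **Side effects, set side by side.**

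| Reaction | Sections 2.3.1 and 9.2.2 | Appendix S |
|---|---|---|
| Tingling | listed | stated |
| Burning | listed | denied |
| Itching | listed | denied |
| Headache | listed | denied |
| Seizure (theoretical, not reported) | listed as a possibility | not mentioned |

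The script names 1 of 4 reported reactions and denies 3. The seizure possibility is omitted, not denied, because the script speaks only of effects that have been found.

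**Visits: reproducing Section 4.** Inputs from Section 4: 1 initial screening, 1 second screening, 0 to 2 further screenings, 5 stimulation days, 2 follow-ups.

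- Minimum: 1 + 1 + 0 + 5 + 2 = 9
- Maximum: 1 + 1 + 2 + 5 + 2 = 11

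This matches the stated 9 to 11.

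**Hours: reproducing Section 4.** Inputs: 2 (initial), 3 (each later screening), 6 (Day 1), 4.5 for each of Days 2 to 4, 9 (Day 5), 2.5 (one week), 5 (one month).

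- Minimum: 2 + 3 + 6 + 3 × 4.5 + 9 + 2.5 + 5 = 41
- Maximum: 41 + 2 × 3 = 47

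This matches the stated 41 to 47, so Section 4 is internally consistent.

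**Visits: the script.** 1 + 5 + 1 + 1 = 8. The shortfall against Section 4 is 9 − 8 = 1 to 11 − 8 = 3 visits, which is 1/9 = 11% to 3/11 = 27% of the Section 4 count. At 3 hours per repeat screening, that is 3 to 9 hours not described to the caller.

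**Is the missing visit optional?** Section 5.1 requires a change in AHRS of no more than 20% across a two-week interval during screening. That needs at least two screening ratings, and Section 7.2 places the second at a separate visit about two weeks after the first. Under Sections 4, 5.1 and 7.2, no completer can finish in eight visits.

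**Where the conflict sits.** The Protocol Summary disagrees with itself. Its text counts 8 visits, yet it allots time to follow-up screening sessions, and its schematic shows four screening sessions, five stimulation days and two follow-ups: 4 + 5 + 2 = 11. Correcting Appendix S alone would leave the Summary and Section 7.1 in conflict with Sections 4 and 7.

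**The case against.** The strongest reply is that the call does little harm. Providers are asked to discuss the study with patients before the call, so it is not the first they hear of it. The call only books the first session. There the consent form is read aloud, comprehension is checked, and written consent covering risks in detail precedes any treatment or assessment (Sections 7.2 and 13.3). This stands, and it limits the consequence to the stage before consent. It does not make the script's sentence true.

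The protocol's uncertainty over whether stimulation causes the mild reactions does not rescue the sentence either. The script says that no other effects have been found, and it attributes tingling to the stimulation.

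A reader might infer three stronger points that the documents do not support:

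- **Shrinkage of the arms of 16.** The uncounted visits are all screening visits. Appendix A marks randomisation in the same column as the first PANSS, BACS and stimulation entries, after screening. For the period after randomisation, the script lists the same visits as Section 4, so anyone randomised has already attended the visits it left out. The removal rule in Section 5.4.2 concerns missed stimulation sessions, which the script counts correctly.
- **A denied seizure risk.** The script is silent about it. Section 2.3.1 calls it theoretical and unreported in humans, so there is no contradiction.
- **Screening for too short a day.** Just before the 8-hour question, the script asks about availability on weekdays from 8 to 5, a 9-hour window that already covers Day 5. The 8-hour figure is inexact, but the caller has been asked about a day of the right length.

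The lower bound of one session is also fair, since a person may stop after the first. The problem is the upper bound.

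**Conclusion.** Wrong as written, at low severity. The side-effect sentence denies three of the four reactions that the protocol lists in two places. The session count is 1 to 3 visits (3 to 9 hours) below Section 4 and omits a screening visit that Sections 4, 5.1 and 7.2 require of everyone. The visit conflict is document-wide: it runs between the Protocol Summary, Section 7.1 and Appendix S on one side and Sections 4 and 7 on the other.

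The effect falls before consent. Candidates decide whether to attend on an inaccurate account of known reactions and burden, and some may drop out during screening. The documents give no figure for how many. Nobody is enrolled or treated on the script alone, and no statistical quantity changes. The conclusion assumes that the script is read as printed, as Section 7.1 directs, and that the removed consent form describes risks in detail, as Section 13.3 says it does.

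**What to change.** 1. In Appendix S, replace the side-effect sentence with the reactions listed in Sections 2.3.1 and 9.2.2.
2. Reconcile the visit count across the Protocol Summary (précis, participation duration and schematic), Section 4, Section 7.1, the visit numbering in Section 7, and Appendix S. The script should then state the full number, including the second and possible repeat screening visits.
3. As minor points in the same edit, reconcile the 8-hour willingness question with the Day 5 length of about 9 hours in Section 4 and the Protocol Summary. Reconcile the length of the first session too (about 3 hours in the script and the Summary text, about 2 hours in Section 4 and the Summary schematic). Correct the appendix reference in Section 7.1.

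The cost is a wording change and a minor IRB submission. A few more people may decline at the call. No treatment, endpoint or analysis is affected.
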